6.2. Lost to Follow up

A participant will be considered lost to follow-up if the participant is unable to be contacted by the study site on POD1.

The following actions must be taken before the participant is considered lost to follow-up:

- Before a participant is deemed lost to follow-up, the investigator or designee must try to regain contact with the participant on postoperative day 1 (by SMS or at least 2 telephone calls)
- Should the participant continue to be unreachable, the participant will be considered to have withdrawn from the study.

7. Study Assessments and Procedures

Study assessment will be done by using a preoperative questionnaire, assessment of postoperative pain during the PACU stay and a postoperative telephone call on POD1. Data will also be collected from the patient's medical journal.

All screening evaluations must be completed to confirm that potential participants meet all eligibility criteria. The investigator will maintain a screening log to record all participants screened and to confirm eligibility or record screening failure, as applicable.

7.1. Safety Assessments

The patients will adhere to standard procedures for ambulatory gynaecological laparoscopic surgery patients.

8. Statistical Considerations

The statistical analysis plan will be finalized prior to start of data collection and it will include a more technical and detailed description of the statistical analyses described in this section. This section is a summary of the planned statistical analyses of the most important endpoints including primary and key secondary endpoints.

8.1. Statistical Hypothesis

The primary objective is to demonstrate that the risk matrix for prediction of postdischarge pain performs well also in newly collected data. i.e. the objective is to validate a previously developed risk matrix in new data sampled from an equivalent patient population.

8.1.1. Multiplicity Adjustment

Not relevant.

8.2. Analysis Sets

All enrolled patients, e.g. those who fulfilled inclusion criteria will be included in the full analysis set (FAS).

8.3. Statistical Analyses

8.3.1. General Considerations

We will compare the collected sample with the previously collected sample on selected baseline variables to assess possible selection bias and generalisability of our results. Due to changes in clinical practise, a majority of patients is now treated with Clonidine, which was not the case when the matrix was developed. To avoid unnecessary delays in recruiting and to ensure that the results will be relevant for todays' patients, we will include patients treated with Clonidine. The previously developed risk matrix will be applied on the data and the predicted and observed outcomes will be compared. In case of under- or over-estimation, the risk matrix will be calibrated.

8.3.2. Primary Endpoint Analysis

The primary endpoint is severe postoperative/postdischarge pain (NRS ≥ 7).

8.3.2.1. Definition of endpoint(s)

This variable is dichotomized as follows: 0=0-6 and 1=7-10.

8.3.2.2. Main Analytical Approach

We will validate the performance of a newly developed risk matrix. We will compare the predicted probabilities of worse postdischarge pain using the risk model with the recorded values. Further, we will perform comprehensive validation. The observed and predicted outcomes will be arranged in a confusion matrix. Further, we will investigate discrimination ability of the model by computing AUC (area under the curve) and c-statistics. Overfitting will be assessed by computing a calibration slope. Finally, we will refit the prediction model and perform tuning of the model parameters. Due to changes in clinical practise, we will include both patients treated and not treated with Clonidine. To investigate the effect of being treated with Clonidine, we will include this variable as a possible confounder.

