1.1. Synopsis

Protocol Title: Validation of a risk matrix for severe postdischarge pain after ambulatory gynaecological laparoscopy

Brief Title: Predicting pain after ambulatory gynaecological laparoscopies

Rationale:

Objectives, Endpoints, Assessments:

Objectives	Endpoints	Assessments
Primary		

 To validate a prediction tool for severe postdischarge pain (NRS 7-10) after gynaecological laparoscopic surgeries 	
 Worst pain since discharge from hospital within 24 h after surgery 	
 Pain assessment using the Verbal Numeric Rating Scale 0-10, on POD1

Study design: Prospective observational cohort study

This study design includes no masking.

Brief Summary:

The purpose of this study is to test and validate a newly developed risk matrix in a new sample of patients. The risk matrix will be a useful tool to preoperatively predict who is at risk for experiencing severe postoperative pain after discharge from ambulatory gynaecological surgery. When validated, the prediction tool will be implemented in everyday clinical practice with ambulatory gynaecological patients.

Study details include:

- The study duration will be up to 6-7 months.
- Data will be collected at three occasions, on the day of surgery, during PACU stay and on POD1.

Number of Participants:

Approximately 207 participants (minimum) will be enrolled in the study.

Schema

Procedure	Day of surgery	PACU	POD1	Notes
Written informed consent	x			
Inclusion/exclusion criteria	x			
Demography/Baseline data	x			Questionnaire
Postoperative pain		x		
Postdischarge pain			x	Postdischarge pain data collected by telephone follow-up
Intraoperative data collection			x	Patients' medical records (Dips and MetaVision)

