2.1. Study Rationale

As day surgery is increasingly preferred over in-hospital treatment due to feasibility and reduced economic costs, it is important to evaluate patient related outcomes such as comfort and safety after discharge. Most previous studies on predictors for postoperative pain have not been focused on postdischarge pain.

Early identification of patients at high risk for severe pain can contribute to better and more targeted individual pain prevention and management, thereby reducing the incidence of unnecessary pain and discomfort after surgery. By identifying and treating patients who are particularly vulnerable to severe postoperative pain, we can also reduce hospital stays, prevent unplanned admissions due to pain, decrease the number of outpatient inquiries related to pain, and expedite recovery and return to normal activities. This will contribute to reduced resource use, improved patient care, and hopefully increased patient satisfaction.

The risk matrix for severe postoperative pain has the potential to improve clinical practice by providing clinicians with a simple, evidence-based tool that can identify high-risk patients before surgery. The scoring takes less than one minute. Today, we do not have such instrument at hand. The results from this project could influence current routines and treatments at OUS and may also be applicable to other patient populations and other hospitals.

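### Implementation depends on validation, but no planned analysis states a risk cut-off or compares use of the matrix with treating all women alike

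*Combined protocol and SAP*

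**What the plan says.** Three statements set the purpose:

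- Synopsis (1.1): "When validated, the prediction tool will be implemented in everyday clinical practice with ambulatory gynaecological patients".
- Study Rationale (2.1): the matrix is to give clinicians a "simple, evidence-based tool that can identify high-risk patients before surgery". That is a classification use, meant to direct prevention.
- Statistical Hypothesis (8.1): the aim is to "demonstrate that the risk matrix for prediction of postdischarge pain performs well also in newly collected data". No figure or rule says what performing well means.

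The analyses are these:

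- General Considerations (8.3.1): "The previously developed risk matrix will be applied on the data and the predicted and observed outcomes will be compared". The matrix is calibrated if it under- or over-estimates.
- Main Analytical Approach (8.3.2.2), on calibration: "Overfitting will be assessed by computing a calibration slope". The same section, on classification: "The observed and predicted outcomes will be arranged in a confusion matrix". Discrimination is to be measured by the AUC and the c-statistic. A refit and tuning follow.
- Sensitivity Analysis (8.3.2.3): the model as developed is evaluated in women with and without Clonidine.
- Supplementary (8.3.2.4) and other (8.3.6) analyses are declared not relevant.

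None of these sections gives a risk cut-off, a performance target, a net-benefit analysis or a comparison with a policy that ignores the matrix.

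**The concern.** The decision that follows the study is whether clinicians should use the matrix to single out women before surgery. The alternative is to treat all women alike, either as if all were at high risk or as if none were. AUC summarises ranking over all cut-offs, and for a yes/no outcome it is the same quantity as the c-statistic. The calibration slope describes whether predictions are too extreme or not extreme enough. Neither says whether acting on the predictions beats a uniform policy.

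A classification table can say so, but only at a stated cut-off and only when set beside the uniform policies. At 40% prevalence this matters: flagging nobody is already 60% accurate, and flagging everybody has 100% sensitivity and a positive predictive value of 40%. Read alone, respectable figures from the table could be taken as support for implementation when they are close to what is achieved with no tool.

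**Working it through.** **Inputs from the protocol (8.5).** Five model terms, 75 events, 40% prevalence, 188 evaluable, 207 enrolled. These reproduce. 75 / 5 = 15 events per term (the 15 is inferred, not stated); 75 / 0.40 = 187.5, rounded up to 188; 188 × 1.10 = 206.8, rounded up to 207. Non-events: 188 − 75 = 113.

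**Assumptions (the documents give neither an AUC nor a threshold).** AUC A = 0.60, varied below; perfect calibration; normally distributed score with equal variance in cases and non-cases; thresholds t from 20% to 50%.

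**Step 1: would the AUC look acceptable?** Hanley-McNeil variance:

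[A(1−A) + (75−1)(a − A²) + (113−1)(b − A²)] / (75 × 113), with a = A/(2−A) = 0.4286 and b = 2A²/(1+A) = 0.4500.

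= (0.240 + 74 × 0.0686 + 112 × 0.0900) / 8475 = 15.39 / 8475 = 0.001816, so SE = 0.0426.

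95% CI: 0.600 ± 1.96 × 0.0426 = 0.516 to 0.684, which excludes 0.5. An observed AUC of about 0.584 is enough for that. The calibration slope is 1 by construction.

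**Step 2: does acting on the tool beat a default?** Let d = √2 × Φ⁻¹(0.60) = 0.358. A calibrated risk of t corresponds to the score cut x = [logit(t) − logit(0.40) + d²/2] / d. Then sensitivity = 1 − Φ(x − d) and false-positive rate (FPR) = 1 − Φ(x).

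Net benefit = 0.40 × sensitivity − 0.60 × FPR × t/(1−t). Flag-all = 0.40 − 0.60 × t/(1−t). Flag-none = 0. Gain = net benefit − the larger of the two defaults.

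Example, t = 0.30: sensitivity 0.921, FPR 0.854, odds 0.4286. Net benefit = 0.3684 − 0.2196 = 0.1488; flag-all = 0.1429; gain = 0.006.

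Example, t = 0.40: sensitivity 0.571, FPR 0.429, odds 0.6667. Net benefit = 0.2284 − 0.1716 = 0.057; both defaults are 0; gain = 0.057.

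| Threshold | Flagged | Gain, AUC 0.60 | Gain, AUC 0.68 |
|---|---|---|---|
| 20% | 99.6% | 0.000 | 0.005 |
| 30% | 88% | 0.006 | 0.031 |
| 35% | 71% | 0.022 | 0.060 |
| 40% | 49% | 0.057 | 0.104 |
| 45% | 28% | 0.028 | 0.075 |
| 50% | 13% | 0.011 | 0.052 |

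(The flagged column is for AUC 0.60.)

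**Step 3: accuracy at a 50% cut-off, AUC 0.60.** Sensitivity 0.170, FPR 0.095: 0.40 × 0.170 + 0.60 × 0.905 = 0.611, against 0.600 for flagging nobody.

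**Step 4: precision of the added analysis.** Simulating 188 women from the same model, the standard deviation of the net-benefit gain is about 0.02 to 0.04 at thresholds of 30% to 50%. A 95% interval is then roughly ± 0.04 (1.96 × 0.02) to ± 0.08 (1.96 × 0.04).

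**The case against.** Discrimination, calibration and classification are the usual components of a validation study, and the stated objective is predictive validity. On that view net benefit is a separate question of utility. This would be a sufficient answer if the synopsis did not carry validation straight into routine use.

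The opening of section 8 calls itself a summary and promises a more detailed analysis plan. The missing items may be intended for that plan; the text available does not contain them.

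A reader might infer four stronger points. The documents do not support them.

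- *That the tool would be of almost no use at 40% prevalence.* This holds only at some thresholds. The same AUC 0.60 tool gains 0.057 at 40%, about ten times its gain at 30%. AUC 0.60 is itself an assumption, and nothing in the documents says the matrix performs that poorly.
- *That the classification table cannot answer the question.* Its counts, with the cut-off, are exactly what net benefit needs, and its margins give the prevalence. The cut-off and the comparison are missing; the data are not.
- *That a negative verdict is impossible.* The developed matrix is applied first, recalibration is conditional, and nothing says that a recalibrated or refitted model counts as validated. The text is silent on the verdict and does not exclude a negative one.
- *That an AUC interval excluding 0.5 is the criterion for success.* No section says this. It shows only how weak a result could still look favourable.

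**Conclusion.** The point stands in a limited form. The plan links validation to implementation and intends the matrix to pick out high-risk women. It fixes neither the cut-off nor the comparison that would show whether doing so improves on a uniform policy.

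Under the stated assumptions (40% prevalence, 75/113, perfect calibration, AUC 0.60), a tool with an AUC interval of 0.52 to 0.68 and a slope of 1 gains between 0.000 and 0.057 in net benefit across thresholds of 20% to 50%. Usefulness therefore turns on the threshold of intended use, which the plan leaves open. This does not show that the matrix is poor; it shows that the planned results alone could not tell a useful tool from one that adds little. The sample size is not affected. The change should be made before analysis.

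**What to change.** In 8.3.2.2, for the unchanged matrix and before any recalibration or refit:

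- State the risk threshold range of intended use, chosen and justified by the investigators before analysis, and the cut-off used for the classification table.
- Report net benefit against flag-all and flag-none over that range, with bootstrap 95% confidence intervals.
- Show the table's accuracy and positive predictive value beside the no-tool values (about 60% and 40% at the anticipated prevalence, replaced by the observed ones).

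In 8.1 and the synopsis, limit the implementation statement so that it rests on the unchanged matrix's discrimination, calibration and net benefit over that range, taken together. A strict rule that the matrix must beat both defaults at every threshold is not advised. With 188 women, a calibrated tool with AUC 0.70 would meet such a rule over 20% to 50% in 5-point steps only about two times in three (64% to 68% across simulation runs, on point estimates).

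The cost is a few lines of text and one extra analysis on data already being collected, with no added patients or visits. The intervals will be fairly wide, and the study may have to report that the matrix adds little.

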8.3.2.3. Sensitivity Analysis

Due to changes in clinical practise, we will evaluate our original model on patients treated and not treated with Clonidine.

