8.5. Sample Size Determination

The logistic regression model which will be validated includes 4 variables and one additional variable to adjust for the possible confounding effect of being treated with Clonidine, thus will require at least 75 patients who report severe post-discharge pain. Based on our

previous research, we anticipate that 40% will report severe postdischarge pain, therefore we aim to include at least 188 patients. Allowing for 10% drop-outs/loss to follow up we aim to include 207 patients. We anticipate including approximately 40 patients monthly, thus we will be able to include 207 patients in 5 to 6 months. This sample size will enable us to perform all pre-planned analyses with sufficient statistical power and provide estimates with sufficient precision.

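### A calibration slope below 1 in the new sample does not by itself show overfitting, because treatment has changed since the matrix was developed

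*Combined protocol and SAP*

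**What the plan says.** Section 8.3.2.2 (Main Analytical Approach) gives the calibration slope a single purpose: "Overfitting will be assessed by computing a calibration slope". The slope is to be computed in newly collected patients. Section 8.1 describes the aim as to "validate a previously developed risk matrix in new data sampled from an equivalent patient population".

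Section 8.3.1 reports that treatment has changed: "a majority of patients is now treated with Clonidine, which was not the case when the matrix was developed". The plan responds to this in four places:

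- Section 8.3.1: "We will compare the collected sample with the previously collected sample on selected baseline variables".
- Section 8.3.1: "In case of under- or over-estimation, the risk matrix will be calibrated".
- Section 8.3.2.2: "To investigate the effect of being treated with Clonidine, we will include this variable as a possible confounder". Section 8.5 counts this extra term in the sample size.
- Section 8.3.2.3: "we will evaluate our original model on patients treated and not treated with Clonidine".

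The plan names no calibration intercept and no confidence interval for the slope. It does not say that the slope will be computed within Clonidine groups, and it gives no rule for telling overfitting from other causes of a low slope.

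**The concern.** A slope below 1 means that predicted risks are too spread out for the patients in whom they are tested. Overfitting at development is one cause. In a new sample the slope isolates that cause only if the predictors act as they did before and the setting is unchanged. Section 8.3.1 says the setting has changed for most patients, and the amendment table gives as its reason that Clonidine could alter how pain is felt after surgery. The plan thus names a second possible cause of a low slope and still ties the slope to overfitting alone.

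What is at stake is the conclusion. Overfitting says that the original coefficients were too large from the start. Changed predictor effects say that the matrix may have been sound for the earlier regimen but carries over less well to current care. The synopsis says the tool is to go into routine use once validated, so readers will want to know which of these was found.

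**Working it through.** **The plan's own figures.** The plan states no slope value or threshold. Its sample size reproduces: 5 variables × 15 events = 75 events (the 15 is inferred from 75/5, not stated); 75/0.40 = 187.5, so 188; 188 × 1.10 = 206.8, so 207. The precision figures below use 188.

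**Assumptions.** The documents give neither the Clonidine share beyond a majority, nor its effect, nor the spread of the model's predictions. Assumed: share 60% or 80%; standard deviation (SD) of the linear predictor 0.8 to 1.3 (AUC about 0.70 to 0.79); event rate without Clonidine 42%, from section 2.2. The original model is made exactly right for untreated women, so there is no overfitting. The slope is b in logit P(severe pain) = a + b × (original linear predictor), fitted to 500,000 simulated women per scenario.

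| How Clonidine acts | Expected slope, all patients |
|---|---|
| No effect | 1.00 |
| Constant effect, unrelated to predictors, OR 0.7 / 0.5 / 0.3 | 0.99–1.00 / 0.97–0.99 / 0.93–0.96 |
| Same ORs, given more often to higher-risk women (log-odds of receipt +1 per SD of risk) | 0.91–0.97 / 0.81–0.93 / 0.67–0.85 |
| Predictor effects cut to 75% in treated women | 0.79–0.85 |
| Predictor effects cut to 50% in treated women | 0.58–0.68 |

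The last two rows can be checked by hand. The pooled slope is close to share × k + (1 − share), where k is the remaining fraction of the predictor effect:

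- k = 0.75: 0.6 × 0.75 + 0.4 = 0.85, and 0.8 × 0.75 + 0.2 = 0.80.
- k = 0.50: 0.6 × 0.50 + 0.4 = 0.70, and 0.8 × 0.50 + 0.2 = 0.60.

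**What the planned Clonidine term does.** In the weakened-effect scenarios, adding Clonidine as a main effect leaves the slope unchanged (for example 0.70 before and after). A main effect shifts the intercept, and no interaction is planned.

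**What the intercept would add.** A constant effect at OR 0.5 lowers the event rate from 42% to about 31–35% with almost no change in slope. Weakened effects, as simulated, leave the event rate at about 41–42% and lower the slope. Slope and intercept together therefore say more than the slope alone.

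**Chance.** With 188 patients the standard error of the slope is about 0.17 to 0.23 for spreads of 0.8 to 1.3, and up to about 0.28 for a spread near 0.63 (AUC about 0.67). The 95% half-width is then 1.96 × 0.17 = 0.33 to 1.96 × 0.28 = 0.55. With a true slope of 1 and spreads of 0.8 to 1.3, about 27 to 32% of simulated samples gave an estimate below 0.9.

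**What the split by Clonidine can show.** Under weakened effects the slope is about 0.75 or 0.50 in treated women and about 1.0 in untreated women, so the split looks in the right place. If 20% are untreated, 0.20 × 188 ≈ 38 women remain. The standard error there is about 0.4 to 0.6, a half-width of about 0.8 to 1.2.

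**The case against.** The strongest reply is that one short sentence is being read too strictly. The plan discloses the treatment change, compares the two samples at baseline, adds a Clonidine term, evaluates the original model by Clonidine status, and recalibrates whatever the cause. No threshold or decision depends on calling the slope overfitting. Section 8 also describes itself as a summary, with technical detail to follow in the SAP. Much of this stands. A reader might infer that the plan blames every shortfall on overfitting, and its other provisions show that it does not.

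A reader might also infer that the matrix will be wrongly called overfitted. The documents do not support that. It requires Clonidine to weaken the predictors or to be given selectively, and neither is documented; a plain constant effect hardly moves the slope. Nor do the documents show that women not given Clonidine today are a selected group, since they say nothing about who goes untreated. The reference to an equivalent population in section 8.1 can fairly be read as being about patient characteristics, as section 3 suggests.

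The reply does not rescue the sentence. It states how the slope is to be read, and that reading is unsafe in an external sample whose treatment has changed. The evaluation by Clonidine status names no measure and may rest on few untreated women, and the main-effect term cannot correct the slope. Nothing in the available text provides the missing interpretation.

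**Conclusion.** Wrong as written, on the interpretation of the slope only. A slope below 1 in the new data may reflect changed predictor effects, selective Clonidine use, case mix, chance or overfitting, and the plan cannot tell these apart from the slope alone. With no overfitting, the pooled slope could lie anywhere from about 0.58 to 1.00 depending on how Clonidine acts. A clear fall requires weakened predictor effects or selective use; a constant effect unrelated to the predictors leaves the slope at 0.97 to 1.00 at ORs of 0.5 to 0.7. These values rest on the assumed Clonidine share, effect sizes and predictor spread. The point that the slope does not identify overfitting does not depend on them.

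**What to change.** In section 8.3.2.2, replace the sentence on overfitting with:

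*The calibration slope and intercept of the original model in the new data will be reported with 95% CI, overall and by Clonidine status, as measures of calibration and transportability to current practice; a slope below 1 will not by itself be attributed to overfitting.*

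This also gives the evaluation in section 8.3.2.3 a named measure.

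Optionally, if a separate estimate of overfitting is wanted, report the optimism-corrected slope from a bootstrap of the development data. It must repeat every model-building step, including the choice of the four factors and the construction of the matrix. It should not serve as a strict attribution rule, because the external slope it would be compared with is imprecise.

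The cost is a change of wording and a little extra analysis, with no new patients or data. The intervals in the Clonidine subgroups will be wide, and the report should say so.

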2.3. Benefit/Risk Assessment

There is no risk connected to participation in the study. All patients will receive standard medical and surgical treatment throughout the study.

3. Objectives, Endpoints, and Estimands

Objectives	Endpoints	Assessments
Primary		
To validate a prediction tool for severe postdischarge pain (NRS 7-10) after gynaecological laparoscopic surgeries	Worst pain since discharge from hospital within 24 h after surgery	Pain assessment using the Verbal Numeric Rating Scale 0-10, on POD1

The primary clinical question of interest is to validate if the risk matrix developed previously using a different data set (i.e., a new population with similar patient and surgical characteristics) can predict severe pain after ambulatory gynaecological laparoscopy.

4. Study Design

Prospective observational cohort study

In this study, we will collect data necessary to validate a previously developed risk matrix, at two different time points: T1) preoperatively on the day of surgery, T2) during a follow-up call on POD1, to collect postdischarge pain data. In addition, patients' postoperative pain will be assessed using the NRS, during PACU stay.

Data to be collected:

- T1: Age, height, weight, living arrangement, education, employment status, financial concerns, smoking status, previous abdominal surgery, dysmenorrhea severity, preoperative pain, preoperative non-opioid analgesics/opioids, postoperative pain-expectation, preoperative anxiety related to surgery, insomnia, previous treatment for anxiety, depression or other psychological disorder.
- T2: Postdischarge pain on POD1: at rest, during activity, average pain, and worst pain since discharge. Non-opioid and opioids consumption after discharge will also be recorded. Any case of unplanned admission or health care contact.
- PACU: worst pain during PACU stay.
- Patients' medical records (Perioperative data): ASA classification, type of surgery, surgery duration, anaesthesia duration, intra- and postoperative medication.

Data will be registered in Nettskjema/TSD.

End-of-Study Definition

The end of the study is defined as having a complete data set for at least 207 patients.

A participant is considered to have completed the study if she has completed all questions including the follow-up call on POD1.

5. Study Population

Women scheduled for ambulatory gynaecological laparoscopy in general anaesthesia.

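### The planned refit and tuning of the prediction model has no internal validation, so a refitted version would look better than it is; validation of the original matrix is unaffected

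*Combined protocol and SAP*

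**What the plan says.** Section 8.3.2.2 (Main Analytical Approach) first assesses the existing matrix. Predicted probabilities are set against recorded outcomes, "The observed and predicted outcomes will be arranged in a confusion matrix", AUC and c-statistic are computed, and "Overfitting will be assessed by computing a calibration slope". Then comes the refit: "Finally, we will refit the prediction model and perform tuning of the model parameters". No condition is attached to it. Clonidine treatment is added to the model as a possible confounder.

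Other sections bear on which model is meant:
- Section 8.1: "the objective is to validate a previously developed risk matrix in new data sampled from an equivalent patient population".
- Section 8.3.1: "In case of under- or over-estimation, the risk matrix will be calibrated".
- Section 8.3.2.3 evaluates the original model in patients with and without Clonidine.
- Section 8.5 says that the model "includes 4 variables and one additional variable to adjust for the possible confounding effect of being treated with Clonidine".
- Section 1.1 (Synopsis): "When validated, the prediction tool will be implemented in everyday clinical practice with ambulatory gynaecological patients".

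No section names resampling, a split sample, shrinkage or a penalty. None says whether the refit uses the new patients alone or adds the earlier cohort, or what tuning consists of. Supplementary analyses (8.3.2.4) and other analyses (8.3.6) are marked as not relevant. The opening of section 8 promises a more technical SAP, but none of that detail is in the documents supplied.

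**The concern.** A model fitted and tuned in a sample performs better there than in new patients. The plan produces such a model as the last step of its main analysis and names nothing that would measure the difference. The one check it describes as addressing overfitting is listed before the refit and cannot do this job for an unpenalised refit in the same data.

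If the refitted model were reported on its apparent performance, its AUC would be overstated and its predicted risks would tend to be too extreme for later patients. A reader of the publication could also take the word 'validated' to cover a model that was developed in the validation sample.

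**Working it through.** **1. The plan's own figures.** Section 8.5 asks for 75 events for 4 + 1 = 5 variables, which is 15 per variable (inferred; the ratio is not stated). The change log supports the inference: 4 × 15 = 60, 60 / 0.40 = 150, and 150 × 1.10 = 165, the former sample size. For five variables, 75 / 0.40 = 187.5, so 188, and 188 × 1.10 = 206.8, so 207. Both stated figures reproduce. After 10% loss, 207 × 0.90 = 186.3 patients and 186.3 × 0.40 = 74.5 events remain.

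An events-per-variable rule governs the fitting of a model. Its use here, with Clonidine counted, suggests that a full refit is intended.

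**2. Why the slope is uninformative for the refit.** Let the refit have linear predictor L = Xb and fitted risks p. Maximum likelihood gives X′(y − p) = 0. The calibration model logit P(y = 1) = a + sL has score equations Σ(y − p) = 0 and ΣL(y − p) = b′X′(y − p) = 0 at a = 0, s = 1. Both hold, so the estimated slope is exactly 1 however overfitted the model is. All 7,200 plain refits in the first simulation below confirmed this.

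**3. Size for a plain refit in the new data alone.** The documents give no AUC and no coefficients, so these inputs are assumptions: 40% events; two standard normal predictors (age, pain expectation), preoperative pain in 50%, opioid use in 15%, and Clonidine in 70% as the fifth term. Relative log-odds are −0.35, 0.45, 0.5, 0.6 and −0.3, scaled to a true AUC of 0.65, 0.70 or 0.75. There were 600 cohorts per setting, each refit tested in 20,000 new patients. Simulation error of each optimism figure is about 0.004.

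| n = 186 | AUC 0.65 | AUC 0.70 | AUC 0.75 |
|---|---|---|---|
| Four terms: apparent / new-patient AUC | 0.666 / 0.634 | 0.713 / 0.688 | 0.759 / 0.739 |
| Four terms: optimism | 0.032 | 0.025 | 0.020 |
| Four terms: median slope in new patients | 0.78 | 0.83 | 0.88 |
| Four terms: slope below 0.8 | 55% | 41% | 30% |
| Five terms: apparent / new-patient AUC | 0.670 / 0.631 | 0.719 / 0.687 | 0.762 / 0.739 |
| Five terms: optimism (from unrounded AUCs) | 0.040 | 0.032 | 0.023 |
| Five terms: median slope in new patients | 0.72 | 0.80 | 0.86 |
| Five terms: slope below 0.8 | 64% | 50% | 35% |

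The End-of-Study Definition in section 4 instead implies 207 complete patients: "The end of the study is defined as having a complete data set for at least 207 patients". At n = 207, optimism is 0.019 to 0.039 and the median slope 0.74 to 0.88, so the choice of n hardly matters.

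**4. Cross-check with a different set-up.** Five independent normal predictors were used, four of them carrying the effect: b = (d/2)(1, 1, 1, 1, 0), with d = √2·Φ⁻¹(AUC), n = 188 and 3,000 cohorts. For fitted weights w, the new-patient AUC is Φ(w·b / (√2|w|)) and the slope is w·b / |w|². Optimism was 0.043, 0.033 and 0.025, and the median slope 0.72, 0.81 and 0.86. Two further runs of the plain refit at n = 186 gave optimism of 0.021 to 0.048 with median slope 0.69 to 0.88, and about 0.03 to 0.05 with about 0.68 to 0.87. Together these support roughly 0.02 to 0.05 and 0.7 to 0.9.

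**5. Milder readings of the refit.**
- *Pooled with the earlier cohort* (size assumed to be 150 / 300 / 600; Clonidine 0% in it): optimism 0.012–0.021 / 0.007–0.014 / 0.001–0.009, median slope 0.84–0.93 / 0.89–0.95 / 0.93–0.97. The lowest values are within simulation error of zero.
- *Intercept-and-slope recalibration only* (frozen model from an assumed earlier cohort of 300): optimism −0.003 to 0.002, median slope 0.97 to 1.02. This is expected, because with a positive slope the ranking of patients does not change.
- *Penalised refit* (cross-validated ridge, n = 186): optimism still 0.020 to 0.040, median slope 1.03 to 1.13.

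Variable selection as a form of tuning was not simulated.

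**6. Does the remedy work?** With 100 bootstrap resamples, the corrected AUCs were 0.634, 0.689 and 0.741 (four terms) and 0.631, 0.688 and 0.738 (five terms). These agree with the new-patient values within simulation error.

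**The case against.** The strongest reply is that the objective is untouched. AUC and calibration slope of the frozen matrix in new patients are external measures and carry no optimism from a later refit. This stands. A reader might infer that the refit undermines the validation itself; section 8.1 and the order of steps in section 8.3.2.2 do not support that.

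A reader might also infer that the sponsor intends to put an unvalidated refitted model into practice. The Synopsis does not say so. Its preceding sentences concern the newly developed matrix, so the tool to be implemented most naturally means that matrix. Only the conditional calibration in section 8.3.1 and the refit leave some doubt.

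Tuning may be just the recalibration of section 8.3.1, in which case almost no optimism arises. This reading is open, although the five-variable sizing points to a full refit. The text does not settle it.

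Technical detail is deferred to a SAP. That lowers confidence but does not remove the point: section 8 presents itself as the summary of the most important analyses, and it includes the refit without any way of assessing it.

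Finally, one might conclude that shrinkage is required. The figures show a trade-off. Shrinking by the corrected slope cuts slopes below 0.8 from 30–64% to 14–33%, but raises slopes above 1.25 from 3–6% to 11–23%. Mean absolute error in predicted risk moves only from 0.057–0.068 to 0.056–0.064. Ridge gives slopes above 1.25 in 22–42%.

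**Conclusion.** The point holds for the refitted model only. Taken as a plain four- or five-term fit in the new data, the planned refit would have an apparent AUC about 0.02 to 0.05 too high and a median slope in new patients of about 0.7 to 0.9, and nothing named in the plan would show it. These sizes rest on an assumed true AUC of 0.65 to 0.75, assumed predictor effects and prevalences, and 40% events. They shrink with pooling and nearly vanish if tuning is recalibration alone.

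Whether the plan should name a measure of average over- or under-prediction is a separate question. Section 8.3.1 already compares predicted with observed outcomes and acts on a difference, and this point does not depend on it. Confidence is medium, because the form of the refit is unstated. This is a cheap improvement, not a flaw in the primary validation.

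**What to change.** In section 8.3.2.2, state that the whole refit-and-tuning procedure will be repeated in bootstrap samples, and that optimism-corrected AUC and calibration slope will be reported beside the apparent values. Writing this down requires saying which data and terms the refit uses and what tuning means.

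In the same section, limit the validation conclusion to the frozen original matrix, and label any recalibrated or refitted model an updated version that needs its own validation. In the Synopsis, make the implementation statement refer to the frozen original matrix.

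Shrinkage or a penalised fit is optional and not part of the fix. If a penalised fit is chosen, the corrected AUC is still needed.

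Cost: a few lines of text and a few hours of analysis, with no new data and no change to the 207 patients. The downside is a slightly lower reported AUC for the refitted model: lower by about the optimism above for a new-data refit, at most about 0.02 if pooled, and practically unchanged for recalibration alone.
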